13.0 Safety of Subjects

We will convene a data safety monitoring board for this trial. This will be an MD psychiatrist or neurologist at MUSC and an RN familiar with Brain Stimulation but not associated with this project. This is not a clinical trial, merely a scan with ultrasound involved.

We will inform the DSMB of any SAEs promptly, and AE's with each annual renewal. In addition, after the first 10 subjects are enrolled we will summarize the AE's and SAE's, if any, and then convene the DSMB to review these and report their conclusions to the IRB. They will then review SAEs and AE's at the termination of the study.

There will be no formal DSM meetings, but the DSM board will be presented the data after 10 subjects have been scanned and then again at study completion.

All adverse events will be recorded at all visit contacts.

The supervising Institutional Review Board (IRB) will be notified of adverse events, risks, or unanticipated problems according to their reporting requirements. If any adverse events are noticed which are not described in the consent or are serious, we will inform the IRB before continuing with the next enrolled subject. Data collected regarding serious adverse events will include the dates of the scan and the AE and presumed relationship to study stimulation and will be updated as new information becomes available; a narrative description also will be provided.

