When I first proposed to do TMS in the scanner over 20 years ago the MUSC IRB required that I be the first test subject, and report back. I did that and am prepared to do that here if that is what is needed. I think this LIFUP is as safe as diagnostic ultrasound, and has enormous research and clinical potential.)

Specific Aims.

- Aim 1.** Test the safety and feasibility of LIFUP to thalamus in healthy volunteers.
- Aim 2.** Characterize the time course and magnitude of thalamic LIFUP-induced analgesia.
- Aim 3.** Identify the brain circuitry (BOLD activity) that thalamic LIFUP changes during induced pain.

Hypothesis.

The anterior nuclei of the thalamus in addition to periaqueductal gray (PAG) and rostral ventromedial medulla (RVM) are integral regions of a supraspinal opioidergic structure that regulate pain perception (4-8). With the capability to influence deep neurological tissues, low intensity frequency ultrasound pulsation can likely modulate this circuit and induce analgesia. LIFUP deep brain modulation is achieved by induction of focused mechanical waveforms that traverse the cranium and underlying brain tissue (19). The low frequency of the ultrasonic wave consequently alters neuronal transmission and causes action potential variations through mechanical means, rather than thermal (20). The purpose of this study is to examine whether stimulation of the anterior nuclei of the thalamus via LIFUP induces analgesia. **We hypothesize that suppression of the anterior nuclei of the thalamus will induce a temporary increase**

in pain tolerance. Moreover, the behavioral changes in pain will correlate with specific regional BOLD changes during pain.

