Researchers have examined the effects of LIFUP in preclinical and clinical settings, confirming its ability to safely stimulate neural tissue⁽¹¹⁻¹⁴⁾, proposing cellular mechanisms for its efficacy⁽¹³⁻¹⁹⁾, and now using LIFUP in human patients⁽²⁰⁾. Monti et al. (2016) described a case study in which they used LIFUP to stimulate a comatose patient's thalamus.⁽²⁰⁾ Two pre-LIFUP assessments rated the patient as being in minimally conscious state (MCS). After sonication, the patient recovered motor and oromotor functions the next day, advancing to full language comprehension and communication by nodding and shaking his head. Five days post-LIFUP, the patient attempted to walk. While this study was neither blinded nor sham-controlled, the first application of therapeutic LIFUP in a human patient was encouraging and we expect more therapeutic applications of LIFUP and potential clinical trials in the future. If LIFUP continues to show clinical potential, it has the potential to supplant the role of DBS without the need for surgery. The key barrier to LIFUP replacing DBS for clinical applications is that by and large, DBS is used in a manner where the device is inserted and turned constantly on without attempting to fundamentally change circuit dynamics or behavior so that you could remove the device. Obviously, patients cannot permanently wear a LIFUP helmet. However, to the degree that we learn how to stimulate in ways that permanently change circuit behavior (LTD or LTP) without ablation, we may be able to substitute several sessions of LIFUP that can train and rewire the brain instead of permanently implanting hardware. LIFUP can certainly stimulate deep and focal and noninvasively and thus may be a key next step in the field of brain stimulation.

Information on the intervention to be studied.

We will be using the Brainsonix Low intensity focused ultrasound pulsation device. (BX Pulsar 1001). Please see the manufacturers description (Technical Summary) along with appendixes about the actual safety of the device itself.

FDA Status of the BX Pulsar 1001 device.

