5.0 Inclusion and Exclusion Criteria/Study Population

Screening Procedures. Prospective subjects (self-referred via flyers, e-mail announcements, and Catalyst advertisements) will be interviewed by the research team over the phone. Questions asked during this phone interview will focus on chronic (and current) medical problems, seizure history, medications, psychiatric disorders, substance abuse, magnetic resonance imaging eligibility and pain history. The inclusion/exclusion criteria will be used to screen-out participants with conditions that might interfere with or confound the research, or that might render participants vulnerable to potentially negative effects of the

laboratory pain procedures. A copy of the screening form is uploaded to the eIRB website. If the participant qualifies for the study and wishes to proceed, then he or she will be invited to a screening visit that will take place in a quiet office in the Institute of Psychiatry. The research procedures, risks and benefits will be explained during this visit. After providing written informed consent to participate, if the participant is female, then she will also receive a pregnancy test. Participants will be paid **\$30** for participating in the screening procedure. Participants meeting inclusion criteria will be invited to participate in the laboratory investigation. If they choose to participate, they will be paid **\$120** for Visit 2 scanning session and **\$120** for Visit 3 scanning session for a total of **\$270**.

Selection Criteria. Participants must meet the following criteria: (1) 18-45 years of age, (2) no seizure history (individual or family), (3) no history of depression, (4) no hospitalizations or surgeries in the previous 6 months, (5) not currently experiencing pain, (6) no history of chronic pain, (7) no metal implants or objects (e.g. pacemakers, metal plates, wires), (8) not pregnant, (9) no alcohol dependence (10) no illicit drug use in the previous 6 months, (11) no known allergy to capsaicin, (12) no history of brain surgery or brain lesions, (13) no history of loss of consciousness (greater than 15 min), (14) no stimulants or medications that lower seizure threshold.

6.0 Number of Subjects – 35

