7.0 Setting

The initial screening, interview, and structural scan (Visit 1) will be on the Center for Biomedical Imaging at [name]. For Visit 2 and 3, the Brainsight targeting will occur on at the Brain Stimulation Lab on the 5th floor of the Institute of Psychiatry. The LIFUP-MRI scanning will be done at [name]

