10.0 Study Design/Methods

10.1. Study Design. Twenty healthy volunteers between 18-65 years of age without history of depression or chronic pain will be recruited to participate in this sham-controlled, double-blind crossover study, all within one session within the MRI scanner. All participants will receive 10 minutes of sham LIFUP, 20 minutes of rest, and 10 minutes of real LIFUP within the MRI scanner using the BXPulsar 1001, Brainsonix Inc. The order will be counterbalanced. The duration of the LIFUP analgesia and BOLD effects will be determined.

10.2. Behavioral Measures. We will begin baseline pain assessments by administering cutaneous hot and cold stimuli via the Medoc Pathway System (Medoc, Durham, NC) using a 30 x 30 mm ATS thermode. There will be two behavioral measures: quantitative sensory testing (QST) on untreated skin and blocks of pain on capsaicin-treated skin.

QST will be done using method of limits testing on the thenar eminence of the right hand. A program will be set up to administer 10 hot stimuli with random durations between each trial. The ATS thermode begins at 32°C and increases by 0.5°C per second. Participants will be asked to press a button in order to signify three different measures: (1) sensory threshold, or the temperature at which the stimulus becomes noticeable, (2) pain threshold, or the temperature at which the stimulus becomes painful, and (3) pain tolerance, or the temperature at which the stimulus becomes too painful to tolerate. Measuring these thresholds will yield information about

A β , A δ , and C fibers, respectively. The device will be set to stop heating at 51.5° C and stop cooling at 0° C to avoid tissue damage. These ten trials will be performed once before and once after each scanning block, either with thalamic LIFUP or 'fake' thalamic LIFUP.

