15.0 Risks to Subjects

fMRI, EEG measures:

There are currently no known risks of exposure to the MRI environment. One known risk, related to MRI, is that strong magnetic fields attract iron or steel metal objects, leading to safety risks, which are minimized by SOPs among which one of the exclusion criteria of this study: any subject with metallic implants making it unsafe to enter the MRI environment cannot be enrolled. There is also a small risk of discomfort linked to exposure to the noise of the magnet and confined environment which might lead, in some people, to feeling of claustrophobia. There is also a risk if the subject is pregnant but we will exclude pregnant subjects.

LIFUP stimulation:

When used at/below intensities deemed safe by the FDA, no significant and persisting side-effects have been reported, as confirmed in healthy volunteers (Legon et al., 2014), brain injury patients (Monti et al., 2016; see also Interim report on safety enclosed in this application) as well as non-human primates (Deffieux et al., 2013), and other animal models (Tufail et al., 2010; Tufail et al., 2011).

In addition, although in the context of a different study, the FDA has granted to the device we will use a status of Category B (that is, safe and effective) Investigation Device Exemption (G130290), on 2/12/2014. Indeed, this is consistent with the known physics and biophysics of our stimulation protocol in which the device is operated at (acoustic) energy levels that are (1) well below those of a typical Pulsed Doppler ultrasound conventionally used in the clinical context in adults and children (by around 40%), and (2) within the energy limits deemed safe by the FDA.

Thermal Pain System: The Medoc pain system has been used safely by [name] and others for over a decade now. The pain is unpleasant but there are limits to the amount of pain, and there have been no adverse events over 5 MUSC IRB approved studies.

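### No scheduled adverse-event contact or window is described after the final ultrasound session, so later events there depend on spontaneous reporting

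*Combined protocol and SAP*

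**What the plan says.** Section 1.0 makes safety the first aim: "Test the safety and feasibility of LIFUP to thalamus in healthy volunteers". Section 13.0 states how adverse events (AEs) are collected: "All adverse events will be recorded at all visit contacts". It also provides for:

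- prompt notice of serious events to the monitoring board;
- revision of serious-event data as more is learned;
- notice to the IRB of any serious or undescribed event before the study moves on to another participant;
- a board review of the data once ten participants have been scanned, and another at the end.

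It gives no AE window, no symptom list and no contact after a session.

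The documents give two pictures of the visits. Section 5.0 pays for screening and then for two scanning visits, the last described as "for Visit 3 scanning session for a total of" $270. Section 7.0 agrees: "For Visit 2 and 3, the Brainsight targeting will occur on at the Brain Stimulation Lab". Section 10.1 instead describes a "sham-controlled, double-blind crossover study, all within one session within the MRI scanner", with order counterbalanced, and Section 16.0 calls the study one scan.

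On later effects, Section 3.0 cites one brain-injured patient given thalamic LIFUP: "After sonication, the patient recovered motor and oromotor functions the next day", and "Five days post-LIFUP, the patient attempted to walk". Section 15.0 says of earlier work that "no significant and persisting side-effects have been reported".

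**The concern.** If AEs are asked about at visits and the last visit is itself a LIFUP session, nobody asks about the hours and days after that session. A headache, a change in mood or thinking, a sensory symptom or a reaction of the capsaicin-treated skin that starts or lasts after the participant leaves would be recorded only if the participant chose to report it.

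Three things are at stake:

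- **The Aim 1 conclusion.** A finding of no AEs would partly reflect when the question was asked.
- **The IRB safeguard in Section 13.0.** Telling the IRB before the next participant works only for events the team knows about.
- **The ten-participant board review.** It could be reassuring because delayed events were never solicited.

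**Working it through.** The plan states no event rate, follow-up length or power for safety, so there is no figure to reproduce. The check is of the schedule, followed by an illustration.

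**1. Is there another paid visit?** Section 5.0 pays $30, $120 and $120. The sum is 30 + 120 + 120 = 270, which is the stated total. No further paid visit is hidden in the schedule, although an unpaid call is not ruled out.

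**2. Who is asked after real LIFUP, under each reading?**

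- *One session (Sections 10.1, 16.0).* No contact after the session is described, so no participant is actively asked after leaving.
- *Two scanning visits (Sections 5.0, 7.0).* The documents do not say how real and sham are allocated to visits. Assume one condition per visit, with order counterbalanced. Half get real LIFUP at Visit 2 and can be asked at Visit 3, after an unstated interval. The other half get it at Visit 3 and have no later contact. That is 20/2 = 10 (Section 10.1 sample size) or 35/2 = 17.5, so 17 to 18 (Section 6.0).
- If both conditions were given at both visits, everyone's last session would include real LIFUP and none would be asked after it.

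**3. How long is the described same-session period (one-session reading)?** Section 10.3 gives 12 blocks of 22 s heat and 22 s rest: 12 × 44 s = 528 s = 8.8 min. Section 10.2 gives ten ramps from 32 to 51.5 °C at 0.5 °C per second: at most (51.5 − 32)/0.5 = 39 s each, or 390 s = 6.5 min in all.

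- Real LIFUP last: 8.8 + 6.5 = 15.3 min.
- Real LIFUP first: 15.3 + 20 (rest) + 10 (sham) + 15.3 = 60.6 min, or 70.6 min if sham lasts 20 min as in Section 10.3.

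These are approximate. Gaps and the interleaved scan have no stated length, and the rest period is assumed not to overlap the testing.

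**4. What does asking later buy?** Let p be the risk of an AE arising in the days after real LIFUP, and s the share of such events that a scheduled contact would record. Then P(at least one actively recorded) = 1 − (1 − p·s)^n. Both p and s are assumptions. The table gives p = 5%, with the range for p = 2% to 10% in brackets.

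| Scenario | n = 20 | n = 35 |
|---|---|---|
| One session, no later contact (s = 0) | 0 | 0 |
| Two visits, half asked at Visit 3 (s = 0.5) | 0.397 (0.182–0.642) | 0.588 (0.297–0.834) |
| Contact after every exposure (s = 1) | 0.642 (0.332–0.878) | 0.834 (0.507–0.975) |

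For example, 1 − (1 − 0.05 × 0.5)^20 = 1 − 0.975^20 = 0.397. The middle row also assumes that Visit 3 falls late enough and asks about the whole interval.

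**5. What would zero events mean?** The upper 95% bound with none observed is 1 − 0.05^(1/n): 13.9% for n = 20 and 8.2% for n = 35. These bounds apply to delayed events only if every participant was asked about them.

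**The case against.** **The plan does not restrict AE recording to visits.** A reader might infer that AEs are collected at visits and nowhere else, so that the study cannot detect a delayed event. The text does not say so. Section 13.0 leaves room for later reports and for revising serious-event data. This stands: later events are unsolicited, not excluded, and the zeros in the table refer to active enquiry.

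**Visit 3 may be a follow-up contact.** On the two-visit reading it comes after a Visit 2 exposure. This stands for those participants, subject to the unstated interval. It does not help those whose last session includes real LIFUP.

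**The case report does not give an AE timescale.** A reader might take the next-day and five-day observations as the required window and divide them by the minutes in the scanner to get a shortfall. The documents do not support that. The observations are functional gains in one brain-injured patient, in a report that Section 3.0 itself says had no blinding or sham control. The five-day item is a later milestone in a recovery already under way. The case makes delayed effects plausible and no more.

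**The safety question may be meant as acute.** Section 4.0 frames it around LIFUP during provoked pain, and the Section 15.0 sentence on persisting effects summarises earlier work. This is fair, but an acute question still needs a stated window, and Section 13.0 has none.

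**Absence is hard to prove.** Sections 2.0, 11.0 and 14.0 and the consent pages are not in the public text, and a follow-up call or reporting instruction could be there. This stands and limits confidence.

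**Conclusion.** The gap is real but bounded. The available text schedules no enquiry after the final LIFUP session. Its extent depends on an unresolved contradiction: all participants under the one-session reading, and about half under the two-visit reading if order is counterbalanced across visits. For the participants affected, Aim 1 can support a statement about the session itself but not about the following days. The IRB pledge and the ten-participant review could both miss delayed events.

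The documents do not show that delayed AEs occur, or when they would. The probabilities above rest on assumed risks and capture shares and only illustrate the value of asking. This is an inexpensive improvement to the first aim, not a flaw that invalidates the study. Confidence is moderate.

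**What to change.** 1. Reconcile Sections 10.1 and 16.0 with Sections 5.0 and 7.0 on the number of scanning sessions, and state how real and sham LIFUP are allocated to them and the interval between visits.
2. In Section 13.0, define the AE window, with its start and its end.
3. Add a scripted telephone or e-mail AE check by existing staff after each LIFUP session, for example the next day and about a week later, with the timing for the sponsor to set. Use one fixed symptom list at visits and checks, and follow open AEs.
4. Limit the Aim 1 conclusion to that window, and report how many participants completed each check.
5. If a follow-up contact already exists elsewhere in the study documents, cite it in Section 13.0.

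**Cost.** One amendment and two short contacts per session: 35 × 2 = 70 with one session, and up to 35 × 2 × 2 = 140 with two. No extra visit or procedure is needed. Expect some non-response and more unrelated AEs on record.

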15.0 Risks to Subjects

fMRI, EEG measures:

There are currently no known risks of exposure to the MRI environment. One known risk, related to MRI, is that strong magnetic fields attract iron or steel metal objects, leading to safety risks, which are minimized by SOPs among which one of the exclusion criteria of this study: any subject with metallic implants making it unsafe to enter the MRI environment cannot be enrolled. There is also a small risk of discomfort linked to exposure to the noise of the magnet and confined environment which might lead, in some people, to feeling of claustrophobia. There is also a risk if the subject is pregnant but we will exclude pregnant subjects.

LIFUP stimulation:

When used at/below intensities deemed safe by the FDA, no significant and persisting side-effects have been reported, as confirmed in healthy volunteers (Legon et al., 2014), brain injury patients (Monti et al., 2016; see also Interim report on safety enclosed in this application) as well as non-human primates (Deffieux et al., 2013), and other animal models (Tufail et al., 2010; Tufail et al., 2011).

In addition, although in the context of a different study, the FDA has granted to the device we will use a status of Category B (that is, safe and effective) Investigation Device Exemption (G130290), on 2/12/2014. Indeed, this is consistent with the known physics and biophysics of our stimulation protocol in which the device is operated at (acoustic) energy levels that are (1) well below those of a typical Pulsed Doppler ultrasound conventionally used in the clinical context in adults and children (by around 40%), and (2) within the energy limits deemed safe by the FDA.

Thermal Pain System: The Medoc pain system has been used safely by [name] and others for over a decade now. The pain is unpleasant but there are limits to the amount of pain, and there have been no adverse events over 5 MUSC IRB approved studies.

